5. ESTIMAND FOR PRIMARY ENDPOINT

The primary estimand is as follows:

- **Population**: The primary analysis population will be defined as all participants defined by the study inclusion/exclusion criteria who fall into the mITT analysis sample: All randomized participants who received at least one dose of both study treatments and completed the baseline NAC Total Nasal Symptom Score (TNSS) assessment.
- **Variable**: The primary endpoint will be the NAC TNSS area under the curve from 0 to 1 hours (AUC_{0-1hr}) at year 3.
- **Intercurrent Events**: No special handling will be employed for intercurrent events including missing data for any reason; data will be analyzed as observed using a treatment policy strategy. Any missing data prior to and including year 3 visit after treatment will be implicitly handled as Missing at Random (MAR) via the primary mixed-effect model described in [Section 9.1.2](#), without explicit imputation.
- **Population-Level Summary**: The population-level summary will be the difference in least square means at year 3 visit between the combination of SLIT and dupilumab arm and the double-placebo arm (analyzed as randomized) from the primary mixed-effect model.

Sensitivity analyses for the primary estimand will modify the handling of intercurrent events as described in [Section 9.1.3](#) below.

6. STUDY SUBJECTS

6.1. Disposition of Subjects

The disposition of all enrolled participants will be summarized in tables and listed.

The numbers and percentages of participants randomized and in each analysis sample will be displayed by randomized treatment group and overall. Reasons for early termination from the study and visit completion statistics will be presented. For participants discontinuing study treatment early, the reasons for discontinuing study treatment early will also be presented for each treatment. The number and percentage of participants randomized will be summarized.

The listing of disposition data will also include dates of the first dose, randomization, last visit, treatment discontinuation, and termination from study. The listing will be sorted by treatment group and subject identifier.

6.2. Demographic and Other Baseline Characteristics

Summary descriptive statistics for baseline and demographic characteristics will be reported for the randomized and mITT samples. Demographic data will include age, sex, race/ethnicity, body weight at screening, and height at screening. Other baseline characteristic variables will include baseline skin prick test wheal size (mm) to grass pollen and other allergens, and baseline grass pollen specific-IgE. Note that baseline skin prick test wheal size (mm) to grass pollen and other allergens will have the negative control subtracted out, for each participant. If this subtraction causes the wheal size to be <0mm, then a value of 0mm will be imputed for analysis purposes.

These data will be presented in the following manner:

- Continuous data (e.g., age and baseline skin prick test wheal size) will be summarized descriptively by mean, 95% confidence interval for the mean, SD, median, first quartile, third quartile, min, and max.
- Categorical data (e.g., sex and race/ethnicity) will be presented as frequencies and percentages.

Demographic and baseline characteristic data will also be listed.

6.3. Prior and Concomitant Medications

Medications will be coded according to the World Health Organization (WHO) Drug Dictionary (version September-2020, or later). Medications reported in this study include any non-study treatment medication taken, including antibiotics and vaccinations.

Medications reported on the CRF will be categorized for analysis as prior, concomitant, or after study treatment by comparing the medication start and stop dates with the first and last dose of study medication dates. Definitions for each type are as follows:

- Prior medications: both the medication start and stop dates prior to the first dose of study treatment date.

- After medications: both the medication start and stop dates after the last dose of study treatment date.
- Concomitant medications: all other medications not classified as prior or after. Concomitant indicates that the medication overlapped with study treatment by at least one day.

Partial or missing medication start and end dates will be imputed using the algorithm in [Appendix 15.3](#).

The number and percentage of participants receiving prior, concomitant, and after medications will be presented. When reporting the number of participants receiving the medication, a participant will only be counted once if they ever received the medication within the drug class. Percentages will be based on the number of participants in the Safety sample.

Also, a separate summary of antibiotics taken concomitantly will be presented, with the number and percentage of participants, as well as the number of distinct courses/episodes of antibiotic use per treatment group. Antibiotics will be searched for using the WHO drug dictionary coding. Separate data listings will be provided for prior, concomitant, and after medications.

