15.3. Algorithm for Partial or Missing Start Dates

Partial or Missing Start Dates:

AE start dates that are partial or completely missing will be imputed using the following algorithm to assign treatment-emergence status. The same applies for partial/missing medical start dates for assigning concomitant status:

1. If the year and month are known:
 - a. If the year and month are the same as the year and month of the treatment start date, impute to treatment start date.
 - b. Otherwise, use the 1st of the month.
2. If only the year is known:
 - a. If the year is the same as the year of treatment start date, impute to treatment start date.
 - b. Otherwise, impute to January 1st of that year.
3. If the date is completely missing, impute to treatment start date.

Partial or Missing End Dates:

Partial AE (or medication) end dates will be imputed using the same algorithm as above for start dates, but with the following modifications:

1. Date of most-recent follow-up (including end of study date) replaces treatment start date
2. Use last day of month if year/month known, or December 31st if only year known
3. Do not impute completely missing end dates, but leave as missing (i.e. ongoing)

Client:	The National Institute of Allergy and Infectious Diseases (NIAID)
Protocol:	ITN084AD GRADUATE

After finalization of the Statistical Analysis Plan (SAP) and post-database lock, one change to the plan was identified, as summarized below:

Section 9.1.1 (Computation of the Primary Endpoint) of SAP v1.0 contained a typographical error (erroneous carriage return) in the area under the curve (AUC) formula. Using the linear trapezoidal rule as expressed in the text, the formula should have had the $(t_i - t_{i-1})$ term in the numerator rather than denominator. The corrected formula is as follows:

$$AUC = \sum_{i=1}^n \frac{TNSS_{i-1} + TNSS_i}{2} (t_i - t_{i-1})$$

where $TNSS_i = TNSS$ at time i , n is the number of timepoints being summed through the 1 hour timepoint, and $(t_i - t_{i-1})$ is the nominal time difference in hours between timepoint i and timepoint $i - 1$ for each of the intervals in the time span.

The erroneous error in the formula was merely a clerical error in the plan and did not impact any primary or secondary study results that utilized AUC calculations; all calculations were conducted according to the correct formula for the linear trapezoidal rule.

Approvals

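### SAP 6.3 and Appendix 15.3 misfile two date patterns: drugs started after the last dose and still ongoing, and drugs or AEs that ended before dosing but whose start is missing or known only to the first-dose year or month

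*SAP*

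**What the plan says.** SAP 6.3 compares each drug's dates with the first and last dose of study treatment. The first two definitions are "Prior medications: both the medication start and stop dates prior to the first dose of study treatment date" and "After medications: both the medication start and stop dates after the last dose of study treatment date". The third takes the remainder: "Concomitant medications: all other medications not classified as prior or after". The section then states what that remainder is meant to be: "Concomitant indicates that the medication overlapped with study treatment by at least one day". The classes feed counts and percentages in the Safety sample, three separate listings, and a summary of antibiotics taken concomitantly.

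For incomplete dates, SAP 6.3 points to Appendix 15.3: "Partial or missing medication start and end dates will be imputed using the algorithm in" that appendix. Its start-date rules include "If the date is completely missing, impute to treatment start date" and "If the year is the same as the year of treatment start date, impute to treatment start date". A start known to the month is likewise moved to treatment start when it falls in the first-dose month. For stop dates the last rule is "Do not impute completely missing end dates, but leave as missing (i.e. ongoing" (closing bracket omitted). No rule compares an imputed start with a recorded stop.

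SAP 10.3 uses the same start-date algorithm for AEs and defines treatment emergence by start date alone.

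**The concern.** The residual class is described as overlap with treatment, but the rules can put a drug there that never overlapped.

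The first pattern needs no unusual data. Protocol 3.1 has a 52-week observation phase after week 104, Protocol 8.3.1 records medications at every visit, and Protocol 6.5 and 11.4 invite participants who stop treatment early to stay under assessment. A drug begun off treatment and still in use at the last contact has no stop date.

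The second pattern needs an incomplete start date together with a stop before dosing. It then yields a record that starts after it ends.

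What is at stake is the reliability of descriptive displays. The after table and listing would omit ongoing off-treatment starts, and the concomitant table and listing would show them as on-treatment use. The concomitant antibiotic summary could include courses with no overlap. An AE that was over before the first dose could be counted as treatment-emergent in an arm.

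**Working it through.** The plan gives no figure to reproduce, so the check applies the written rules to example dates.

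**Inputs.** The class definitions come from SAP 6.3 and the imputation rules from SAP 15.3. Under Protocol 8.5 the baseline NAC falls in September to January, and Visit 0 follows at least 28 days later and before the end of February. SAP 9.2.6 makes 2021 the baseline season and 2022 year 1. First doses therefore run from about 29 September 2021 (1 September + 28 days) to February 2022.

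**Assumed participants**, chosen inside those windows, with last dose = first dose + 104 × 7 = 728 days:
- A: first dose 20 Jan 2022, last dose 18 Jan 2024.
- B: first dose 15 Nov 2021, last dose 13 Nov 2023.

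**Rules as coded.** Prior: start < first dose and stop < first dose. After: start > last dose and stop > last dose. Concomitant: anything else. A missing stop satisfies neither inequality on stop.

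| Date pattern | A | B | Correct class |
|---|---|---|---|
| Start 1 Jun 2024, no stop (ongoing) | concomitant | concomitant | after |
| Start 1 Jun 2024, stop 31 Jul 2024 | after | after | after |
| Start 1 Jun 2024, stop known to month (Jul 2024) | after | after | after |
| Start 1 May 2021, stop 31 Jul 2021 | prior | prior | prior |
| Start May 2021 (month only), stop 31 Jul 2021 | prior | prior | prior |
| Start 2018 (year only), stop 31 Jul 2021 | prior | prior | prior |
| Start 2021 (year only), stop 31 Jul 2021 | prior | concomitant | prior |
| Start missing, stop 31 Jul 2021 | concomitant | concomitant | prior |
| Start known to first-dose month, stop on the 5th of that month | concomitant | concomitant | prior |
| Start 1 May 2019, ongoing | concomitant | concomitant | concomitant |

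**Pattern 1.** The drug starts 135 days after A's last dose (13 + 29 + 31 + 30 + 31 + 1) and 201 days after B's (17 + 31 + 31 + 29 + 31 + 30 + 31 + 1). Overlap is zero, yet both are filed as concomitant.

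**Pattern 2.** With the start missing, the imputed start falls after the recorded stop of 31 July 2021 by 31 + 30 + 31 + 30 + 31 + 20 = 173 days for A, and by 31 + 30 + 31 + 15 = 107 days for B. In the month-only case the gap is 20 − 5 = 15 days for A and 15 − 5 = 10 days for B. The year-only 2021 start fails for B but not for A, because it depends on the first dose falling in 2021.

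**AEs.** Protocol 12.4.1 collects all AEs from the baseline NAC, at least 28 days before the first dose. An AE in that interval with a known end before dosing and a missing start has its start set to the first-dose date. SAP 10.3 then counts it as treatment-emergent.

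**The case against.** The best defence of pattern 1 is that the appendix equates a missing stop with ongoing, and an ongoing drug that began after the last dose must end after it. Read with the overlap sentence in 6.3, that points to the after class, and a sensible programmer might code it so. This shows what was probably meant. It does not remove the fault, because no sentence says so and the literal definition needs a stop date that does not exist.

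For AEs, moving an unknown start to the first dose errs towards counting the event. That is reasonable when the end is unknown or falls after dosing. It is not needed when a recorded end shows the event was over before the first dose.

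The limits on consequence stand. The primary estimand uses a treatment-policy strategy, the per-protocol sample uses dosing compliance, and no efficacy model uses the medication class. Participants are counted once per drug class, and rescue drugs are dispensed in the on-treatment 2022 and 2023 seasons, so a misfiled pre-treatment antihistamine changes a count only for someone who used none of that class on treatment.

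A reader might infer that the after table is the only by-arm view of year-3 medication, so that the year-3 result cannot be checked against background drug use. The documents do not support this. SAP 9.2.6 analyses the weekly medication score for antihistamines and nasal spray by arm, year and week, including 2024. Protocol Appendix 7 also requires washout of these drugs before the challenge (5 days for antihistamines, 14 for nasal corticosteroids). The weekly score does not cover other drugs or out-of-season use.

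**Conclusion.** The point holds for the two stated patterns on the literal text. Every off-treatment start without a stop date is filed as concomitant. So is every pre-dose drug with a known stop and a start that is missing or known only to the first-dose year or month. An AE with that second pattern becomes treatment-emergent. Each medication result contradicts the SAP's own meaning of concomitant.

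A reader might infer that drugs stopped before the first dose are misfiled in general. They are not: complete dates, or a partial start in an earlier month or year, give the correct class.

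The number of affected records cannot be stated, because the documents give no frequency of missing dates. The example dates are assumptions inside the protocol windows, but the results for pattern 1 and for missing or first-dose-month starts do not depend on them. The affected outputs are the prior, concomitant and after tables and listings, the concomitant antibiotic summary, and treatment-emergent AE counts. No efficacy estimate or p-value changes.

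**What to change.** In SAP 6.3, define after as a start date later than the last dose, whatever the stop date and including ongoing drugs. Define prior as a stop date earlier than the first dose. Concomitant then holds what remains.

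In SAP 15.3, add that an imputed start date may not be later than a known stop date, for medications and AEs alike.

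Under these rules the ongoing year-3 drug moves to after, the incomplete-start cases in the table move to prior, the AE case becomes pre-treatment, and the complete-date cases stay where they are.

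The cost is about three lines of wording and minor programming, with no new data. The SAP already carries a post-lock note correcting the AUC formula, and the same route would serve here. If the tables have already been produced, that note should state how ongoing drugs and start-after-stop records were programmed. A further by-arm table of drugs used between the last dose and S14 is optional and not part of this correction.

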6.4. Medical History

Medical history will be listed, including the verbatim investigator description of the relevant medical condition, the body system (as collected on eCRF), start date, end date, and whether or not the condition is ongoing.

7. STUDY OPERATIONS

7.1. Protocol Deviations

A protocol deviation is any noncompliance with the clinical trial protocol or International Council for Harmonisation (ICH) of Technical Requirements for Pharmaceuticals for Human Use Good Clinical Practice requirements. The noncompliance may be either on the part of the participant, the investigator, or the study site staff. Protocol deviations will be recorded on the source documents and with an explanation for the deviation.

Protocol deviations will be listed separately for randomized and non-randomized participants with information such as type of deviation, severity of the deviation (major or non-major), date of occurrence, the reason for the deviation, steps taken to address the deviation, and whether or not the deviation was IRB reportable. The number of major protocol deviations, the number of each category of violation, the number of consented participants with at least one deviation, the number of deviations leading to termination of a participant from study and the number resulting in an AE will be summarized.

7.2. Randomization

Participants who met eligibility criteria and chose to enroll underwent a baseline visit and then were randomized 1:1:1 to three parallel treatment arms as follows:

- Combination of SLIT and dupilumab
- SLIT plus dupilumab placebo
- SLIT placebo plus dupilumab placebo (i.e. double-placebo)

A listing of treatment assignments, including the randomized arm and actual treatment received will be provided following the final database lock.

7.3. Measurement of Treatment Compliance

Treatment compliance will be summarized by treatment arm through the total duration of study treatment (104 weeks). In each of the treatment arms, compliance rate will be calculated using the following formula:

$$\text{Compliance (\%)} = \frac{\text{observed doses taken}}{\text{expected number of doses}} \times 100$$

The observed doses taken for each study treatment will be calculated as follows:

- SLIT and SLIT placebo: participants were asked to return used SLIT and SLIT placebo blister packs and unused tablets at each study visit. The number of empty blisters was collected, along with a participant-reported quantity taken and a reliability grade for the participant-reported quantity recorded. The observed doses taken will be calculated in two ways:

- Primary method: the total sum of a) the participant-reported quantity taken if the reliability grade = “reliable” plus b) the number of empty blisters returned if the reliability grade of the participant-reported quantity is not “reliable”, across all dispensing/return visits
- Supportive method: the total sum of number of empty blisters returned, across all dispensing/return visits
- Dupilumab and dupilumab placebo: the total sum of injection records where injection date is non-missing

The expected number of doses for each study treatment are as follows:

- SLIT and SLIT placebo: planned to be taken once per day for 104 weeks, which means:
 - *Expected number of doses* = 104 weeks × 7 days per week = 728 doses
- Dupilumab and dupilumab placebo: planned initial subcutaneous injection of 600mg (counted as two doses) at Week 0 followed by a single injection of 300mg every two weeks after for remaining 104 weeks, which means:
 - *Expected number of doses* = $2 + \left(\frac{104}{2}\right) = 54$ doses

8. GENERAL ANALYSIS AND REPORTING CONSIDERATIONS

The following is a list of general analysis and reporting conventions that will be used:

- Categorical variables will be summarized using counts (n) and percents (%) and will be presented in the form n (%). Percentages will be generally rounded to one decimal place.
- In general, first moment statistics, such as the mean, will be reported at 1 more significant digit than the precision of the data. Second moment statistics, such as standard deviation, will be reported at 2 more significant digits than the precision of the data. Other descriptive statistics related to the shape of the data, such as median and range (min/max), will be reported at the same level of precision as the data is recorded. The level of precision may be modified from this convention for specific displays based on clinical judgement.
- Following SAS[®] default rules, the median will be reported as the average of the two middle numbers if the dataset contains an even number of observations.
- Test statistics including *t* and *z* test statistics will be reported to two decimal places.
- Unless otherwise specified, all statistical tests will be 2-sided using type I error rate = 0.05. Estimates and confidence intervals will be reported to 1 more decimal than the original data. *P*-values will be reported to 3 decimal places. *P*-values less than 0.001 will be displayed as “<0.001”; *p*-values greater than 0.999 will be displayed as “>0.999”. A *p*-value will be reported as 1.000 only if it is exactly 1.000 without rounding.
- No preliminary rounding should be performed; rounding should only occur after analysis. To round, the digit to right of last significant digit will be considered: if < 5 then it will be rounded down, if ≥ 5 then it will be rounded up.
- All analysis will be performed using the SAS System version 9.4.

If departures from these general conventions are present in the specific evaluations section of this SAP, then those conventions will take precedence over these general conventions.

8.1. Standard Calculations

The following standard calculations will be used:

- For purposes of longitudinal analyses of efficacy and key safety, the baseline value (unless otherwise noted) is defined as the last observed data value prior to receiving the first study treatment for treated participants. The baseline derivation can include unscheduled visits. In cases where there is not an actual time collected nor timepoint for the assessment of interest, an assessment date on the same date as the *first study treatment date* will be included for the baseline derivation.
- *First study treatment date* is defined as the earliest of: 1.) first SLIT or SLIT placebo treatment date and 2.) first dupilumab or dupilumab placebo injection date.

- Calculations using dates will be performed as noted below.
 - Study day for dates \geq first study treatment date

$$\text{Study Day} = \text{Date} - \text{First study treatment date} + 1$$

Note: Therefore, the first day of study treatment will be considered Day 1.

- Study day for dates prior to first study treatment date

$$\text{Study Day} = \text{Date} - \text{First study treatment date}$$

- Total duration of days

$$\text{Duration} = \text{End date} - \text{Start date} + 1$$

- Values reported as greater than or less than some quantifiable limit (e.g., “< 2.0”) will be summarized using the numeric equivalent, e.g. “<2.0” will be analyzed as 2.0 in summary tables and figures. When this occurs, a footnote will be added accordingly.

8.2. Multicenter Studies

This is a single site study.

8.3. Assessment Time Windows

All scheduled study visits will aim to occur within the time limits specified in Section 8.5 of the protocol. Unscheduled visits may also occur throughout the study.

For summaries, all data will be associated with the nominal study visit for which it was collected. Repeat assessments and unscheduled (including early withdrawal) visits will be included in study listings and may be separately summarized in tables, but will not be used in place of nominal timepoint data. In the case that an early withdrawal visit overlaps with the window for a missing scheduled visit, then it may be used in substitution of the scheduled visit data, if deemed appropriate to do so. Note that no efficacy endpoint data is planned to be collected at unscheduled (including early withdrawal) visits. For scheduled visits, it is not expected that there will be multiple measurements that occur within the same assessment time window. Should that occur, the closest measurement will be used in the analysis; an earlier measure will be used in case of a tie.

